Data Acquisition. Our group has published extensively using resting state connectivity outcomes in both cross-sectional participant-control^{144,155,156} and longitudinal treatment trials.¹⁴²⁻¹⁴⁴ In brief, participants will undergo two resting state fMRI scans; one will be at the beginning of the scanning session and the second will immediately follow the evoked low back pain maneuvers. Ten minutes of resting state fMRI data will be acquired using a T2*-weighted multiband echo planar imaging (EPI) sequence (TR/TE:720/33 ms, flip angle (FA) = 52°, matrix size 90x90 with 60 slices encompassing whole brain, field of view (FOV) = 180 mm x 208 mm, 2.0x2.0x2.0 mm voxels and 833 volumes, MB factor 8). During the resting state fMRI participants will be instructed not to focus on any particular task and stay awake with their eyes open and focused on a fixation cross. Since cardiac and respiratory fluctuations are known to influence brain connectivity,¹⁵⁷ these data will be collected simultaneously using a chest plethysmograph and infrared pulse oximeter. Only participant functional data of less than 2 mm of head motion inside the scanner will be included for analysis.

Preprocessing: fMRI data are preprocessed using fMRIprep (version 1.1.8)¹⁵⁸ running on the high-performance computing resources at our institution. Briefly, preprocessing steps include physiological noise removal (RETROICOR), motion correction, realignment, co-registration, normalization to standard MNI template, regression of nuisance variables (CompCor, motion parameters), and spatial smoothing (FWHM Gaussian kernel of 8mm).

Seed and Network (ICA) Connectivity Analysis. Seed to whole brain functional connectivity analysis is performed using the Conn (Cognitive and affective neuroscience laboratory, MIT, Cambridge, USA) functional connectivity toolbox. Seed regions (5 mm spheres) are chosen based on previously published fMRI studies of chronic pain, including: the insula,¹⁴⁶ and S1/M1.^{154,159} Network seeds (DMN and SLN) will be derived from ICA, as previously published.^{144,145,160} White matter, CSF, and motion parameters are used as covariates of no interest. Data is band pass filtered (0.01-0.1Hz) to remove linear drifts and high frequency noise from the data. First level analysis will correlate the time course from the seed/network to all brain voxels creating connectivity maps for each seed or network.

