## 5 Study Methods

### 5.1 General Study Design and Plan

We will conduct a 36-week pragmatic trial in a cohort of cLBP patients (see Figure 1 and Figure 2). The proposed SMART will consist of a 4-week run-in period using an online cognitive-behavioral self-management intervention (PainGuide), followed by two 8-week treatment periods. All participants will be followed for a total of approximately nine months.

At baseline (T1), approximately 500 patients will undergo a comprehensive baseline phenotyping assessment. After receiving PainGuide (access to an online self-management program) for 4 weeks, each participant will complete a light phenotyping assessment (T2) and a subset of these patients (n=160) will complete an additional deep phenotyping assessment. Those who still have significant pain interference ( $\geq 2$  from Patient Global Impression Scale, PGIC) will be randomized to one of the four 8-week long interventions (i.e., Mindfulness-Based Stress Reduction (MBSR), Physical Therapy (PT)/Exercise, Acupressure self-management [eHealth app], or Duloxetine). Participants with a PGIC=1 will not be randomized and continue with long-term follow-up. The PainGuide run-in is designed to provide the lightest “touch” intervention and to help control for regression to the mean. We will use block randomization with random block size of 4 and 8. Approximately 102 patients will be assigned to each treatment group including Physical Therapy/Exercise, MBSR, Acupressure, and Duloxetine treatment groups. For addition details, please see Section 6.3.

Following the first 8-week treatment period, patients will be reassessed (T3) using light only or light plus deep assessments (for the subset of 160) and those still having significant pain interference ( $\geq 2$  from Patient Global Impression Scale [PGIC]) will be re-randomized to receive one of the three treatments they did not receive in the first treatment period. Participants with a PGIC=1 will not be randomized and continue with long-term follow-up. After the second intervention and three months later, all undergo the light phenotyping follow-up assessment protocol (T4). Lastly, a final assessment will take place at 3 months after the scheduled end of the second 8-week treatment period (T5). There will also be a series of interim assessments that take place at 2-week intervals in between the regular assessments (T1-T5).

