### 6.1 Power for explaining treatment effects

Consider a regression model for correlating within-patient improvement (primary: change in PROMIS Pain Interference; secondary: change in PEG, PGIC; many others as exploratory, see below for details) due to one of the 4 main treatments with a phenotypic variable. Using a two-sided test for correlation at 5% significance level we conclude that we will have the power of at least 80% to detect correlations of 0.28 or higher, conservatively assuming the model is applied to one randomized treatment segment with 102 patients. This corresponds to first phase or second phase treatment in one of the 4 treatment groups, and a model based on the light phenotyping target patient group of 408 total. Similar analysis for the smaller subgroup based on 40 patients with available deep phenotyping for a specific treatment and segment shows that correlation of 0.42 or higher will be detectable with 80% power. This is well within reach as evidenced by available literature on the association between treatment effects and phenotype variables. For example, mindfulness and pain responses showed correlations of 0.43-0.51 in prior reported studies. Our previous studies of the association between pain centralization and analgesic responses in knee osteoarthritis showed similar or higher correlations.

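### SAP 6.1 claims its power for the first or the second phase, but the per-treatment sizes behind it (102 light, 40 deep) hold on average in the second phase only if nobody reaches PGIC=1 at T3

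*SAP*

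**What the plan says.** SAP 6.1 considers a regression of within-patient improvement under one treatment on one phenotypic variable. The test is specified as "Using a two-sided test for correlation at 5% significance level". The light result is "power of at least 80% to detect correlations of 0.28 or higher", obtained by "conservatively assuming the model is applied to one randomized treatment segment with 102 patients". The scope is then set: "This corresponds to first phase or second phase treatment in one of the 4 treatment groups", with a model based on the "light phenotyping target patient group of 408 total". For the deep subset, 80% power at a correlation of 0.42 is claimed for a "smaller subgroup based on 40 patients with available deep phenotyping for a specific treatment and segment".

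Protocol 18.1.5, in its paragraph on power for explaining treatment effects, makes the same first-or-second-phase statement. Its figures are 86% at r=0.3 with 100 patients, and 81% at r=0.43 with 40 deep patients.

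Three other parts of the SAP fix who is in each phase:

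- Section 6 counts the 102 per initial treatment. The patients must have PGIC≥2 at T2 and have completed T1 to T4. There is no condition on PGIC at T3.
- Section 5.1 re-randomises at T3 only those with PGIC≥2. For the rest: "Participants with a PGIC=1 will not be randomized and continue with long-term follow-up".
- Section 7.2.1 confirms that patients may be randomised twice, once or not at all, depending on PGIC.

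**The concern.** The sample size in 6.1 is a first-phase count, but the sentence carries it into the second phase. The second phase draws only on patients who did not reach PGIC=1 after their first treatment, and nothing in either document tops it up. A total of 408 (deep: 160) is therefore the most the second phase can hold, not what it should be expected to hold.

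A reader of 6.1 would take a moderator analysis within one second-phase treatment to have about 80% power, and might read a null result there as more informative than it is. Second-stage data do enter the moderator work, through the joint T3/T4 model (SAP 9.1.1, carried over to the deep measures in 9.1.2) and the exploratory model in SAP 9.2.

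**Working it through.** **Inputs.** Two-sided α=0.05; light r=0.28, n=102, total 408; deep r=0.42, n=40 (SAP 6.1); deep total 160 (SAP 5.6). The share q with PGIC=1 at T3 is not in the documents, and I assume 5% to 30%. The nearest figure, in Protocol 18.1.5, expects at least 30% of patients to improve by 50%, which is a different criterion from PGIC=1.

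**Formula.** By Fisher's z, power ≈ Φ(atanh(r)·√(n−3) − 1.96); the opposite tail is negligible. I also give the power of the t test under bivariate normality.

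**The plan's own figures.**
- Light: atanh(0.28)=0.2877 and √99=9.950. The product is 2.862, so power = Φ(0.902) = 81.7% (bivariate normal 82.0%). This meets the stated minimum of 80%.
- Deep: atanh(0.42)=0.4477 and √37=6.083. The product is 2.723, so power = Φ(0.763) = 77.7% (bivariate normal 78.8%; treating the predictor as fixed, 81.4%). This is close to the stated 80%.
- Protocol: r=0.30 with n=100 gives 86.2% (stated 86%); r=0.43 with n=40 gives 80.9% bivariate normal (stated 81%).

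**Second-phase size.** The number re-randomised is 408(1−q), shared among four treatments, so the average is 408(1−q)/4 = 102(1−q). For the deep subset it is 160(1−q)/4 = 40(1−q). Single arms can vary around the average, because patients eligible for only three treatments have two options left at T3. The four arms together cannot reach 408 if anyone has PGIC=1.

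**Second-phase power** (Fisher z / bivariate normal), and the correlation detectable with 80% power (bias-corrected Fisher z):

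| q | light n | power at r=0.28 | detectable r | deep n | power at r=0.42 | detectable r |
|---|---|---|---|---|---|---|
| 0 | 102 | 81.7% / 82.0% | 0.273 | 40 | 77.7% / 78.8% | 0.426 |
| 5% | 97 | 79.7% / 80.1% | 0.280 | 38 | 75.4% / 76.6% | 0.436 |
| 10% | 92 | 77.5% / 77.9% | 0.287 | 36 | 73.0% / 74.2% | 0.447 |
| 20% | 82 | 72.5% / 73.0% | 0.303 | 32 | 67.4% / 68.8% | 0.472 |
| 30% | 71 | 66.0% / 66.6% | 0.325 | 28 | 61.0% / 62.5% | 0.501 |

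**Break-even, light.** At r=0.28, 80% power needs 98 patients by Fisher z and 97 by the bivariate-normal calculation. That is a responder share of 1−98/102 = 3.9% or 1−97/102 = 4.9%.

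**Protocol version.** With 100 per treatment and r=0.30, q=5% gives n=95 and 84.3%; q=30% gives n=70 and 71.7%.

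**The case against.** The strongest reply is that no planned analysis uses the second phase alone. The primary endpoint is the T2–T3 change. Objective 1 models T3 and T4 jointly and falls back to stage 1 data if the joint assumptions fail (SAP 9.1.1). The mediation analyses use no second-stage data (SAP 9.3). This stands, and it limits the consequence: no sample size or decision changes. It does not rescue the sentence, which names the second phase explicitly.

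The size of the loss also depends on a share the documents omit. PGIC=1 means very much improved, a demanding category. At q=5% light power is still about 80%. The fall in n is certain once there is any responder, but a clear fall below 80% in the light group is not.

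Several stronger readings are tempting, and the documents do not support them:

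- **A further 15% loss in the light group.** A reader might subtract the missing-data ceiling in SAP 7.4 as well. SAP 6 already defines the 102 as available for analysis with T1 to T4 completed, and SAP 7.1 describes the 408 as after drop-out. Subtracting again would count drop-out twice. (SAP 5.4.1 and 5.5 describe 408 as the number randomised; 6.1 uses the target group of section 6.)
- **A lower analysable number for the whole deep subset.** The rule "Only participant functional data of less than 2 mm of head motion inside the scanner will be included for analysis" concerns functional imaging, and the Cramér-Rao limit in Protocol 10.2.2 concerns spectroscopy. SAP Table 3 also lists sensory-testing, blood, heart-rate and actigraphy measures that neither rule touches. The 15% is a general ceiling, not a deep-subset loss rate, and 6.1 specifies 40 with deep phenotyping available.
- **The word *conservatively* is wrong.** It can fairly mean using one segment rather than the joint two-stage model, and in that sense it is right.
- **The whole deep shortfall is due to attrition.** At n=40, before any loss, Fisher z gives 77.7% and the bivariate-normal calculation 78.8%. One to two points of the gap from 80% are method.

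Finally, Protocol 2.1 and 8 assign 110 per arm, although Protocol 4 and the power paragraph use 100. With 110 and q=10%, n=99 and power at r=0.30 is 85.8%, close to the stated 86%. The Protocol range above therefore holds for its own stated 100.

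**Conclusion.** The statement is wrong as written for the second phase. Given any PGIC=1 patient at T3, the average second-phase group is smaller than 102 (deep: 40), and this follows from the SAP's own design. Over an assumed q of 5% to 30%, light power at r=0.28 runs from about 80% to 66%. Deep power at r=0.42 runs from about 75% to 61% by Fisher z, or 77% to 63% by the bivariate-normal calculation. The fair comparison for the deep figures is the 78% to 79% that these methods give at n=40. These ranges rest on the assumed q.

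A reader might infer that the trial is underpowered for its main question. It is not shown to be: first-phase light power reproduces and is untouched. The fault lies in the stated scope of the power claim and is inexpensive to correct.

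**What to change.** In SAP 6.1, do one of the following:

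1. Limit the power statement to the first phase.
2. Keep the second phase, state an assumed share with PGIC=1 at T3, and give second-phase n and power separately, for example as the table under the working.

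Treat the deep subset in the same way, and name the power method used, since it moves the deep figure by a few points. Make the matching change in Protocol 18.1.5, using its own per-arm number. The word *conservatively* can stay if it is tied to one segment versus the joint model.

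The cost is a few lines of text and less favourable second-phase figures. No extra patients and no change to the design or the analyses are needed.

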## 7 General Analysis Considerations

### 7.1 Timing of Analyses

Three interim analyses (safety endpoints) and one final analysis (primary and secondary endpoints) will be conducted. The interim analyses will occur after each consecutive group of another 102 evaluable patients has completed their treatments (408 target group patients total under active treatments after drop-out). The final analyses will be conducted after the 408 target group participants have completed their respective planned visits.

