### 7.2.3 Safety Population

The safety population includes all patients who enter the study at study period T1. Safety analyses will use the safety population to assess the rate of adverse patient events. Safety analysis will be done based on adverse event rates for the whole safety population regardless of their treatment assignments or actual treatments.

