## 10 Safety Analyses

Even though no serious side effects are expected from the treatments, in addition to the safeguards in the SMART trial of the Research Project, the Core will monitor safety periodically with 3 interim analyses and one final analysis, using the Fleming design. The analysis will occur after each consecutive recruitment group of another 102 patients has completed their treatments (408 planned patients total under active treatments after drop-out).

Although it is highly unlikely that there will be extensive adverse events related to the study treatment that is any grade 2 or higher because these are all commonly used treatments for cLBP, we have established an alarm procedure. The alarm procedure is designed to give early warning if the rate of any related AEs, grade 2 or reaches 15% or above. The standard rate is assumed to be 10%. We will consider an alarm when more than 21, 31, 41, and 51 patients show adverse events and classify as related events and are a grade 2 or higher at the 3 interim tests and the final analysis, respectively. If the rate of adverse events is indeed at 15% or higher, the suggestion to stop the trial will be generated by this procedure at 253 treated patients or less on average. Errors of both types are set at 5%. A decision that the rate is safe will be suggested after 265 patients on average.

Events that may require the study to be discontinued or participant to be withdrawn from the study are described in the Protocol Section 18.1.6 and Section 22.

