### 10.1 Adverse Events

An AE will be defined as any unfavorable or unintended change in structure, function, signs, or symptoms temporally associated with the conduct of this study whether or not a causal relationship with the study has been established. The participants will be asked to spontaneously report any AE. Date of onset and resolution (if applicable) of the AE will be documented. The PIs will monitor all AEs to the termination of subject involvement in the study or to a satisfactory resolution if the AE is ongoing.

Events will be considered study-related if classified by the PIs as definitely not, probably not, possibly, probably, or definitely related according to the definitions in Table 7.

Table 7 Defining Relatedness for Adverse Events

Relatedness	Definition
Definitely	The event is definitely not associated with study.

Not	
Probably Not	The temporal association, patient history, or clinical condition is such that the study is not likely to have had an association with the observed event.
Possibly	The event: a) follows a reasonable temporal association with the study procedures, but b) could have been produced by the patient's clinical condition or other therapy.
Probably	The event: a) follows a reasonable temporal association with the study conduct, b) abates upon discontinuation of study procedures, and c) cannot be reasonably explained by the patient's clinical condition or other therapy.
Definitely	The event: a) follows a reasonable temporal association with the study, b) abates upon discontinuation of study procedures, c) cannot be reasonably explained by the patient's clinical condition or other therapy, and d) reappears on re-exposure to the study intervention/procedures.
Unknown	Not enough information exists for the assessment of causality at the time of occurrence.

Signs and symptoms will be graded by the PIs as mild, moderate, severe, or life threatening according to the definitions below (Table 8).

*Table 8 Defining symptom severity for adverse events*

Grade	Definition
Mild	Causing no limitation of usual activity
Moderate	Causing some limitations of usual activities
Severe	Causing inability to carry out usual activities
Life-Threatening	Patient was at immediate risk of death from the event

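### The safety alarm counts give the stated 5% false-alarm rate at 102/204/306/408 patients counted, but the SAP does not say who is counted, and its 5% type II error is about 8% even at those sizes

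*SAP*

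**What the plan says.** SAP 10 sets up a Fleming design with three interim safety looks and a final one. The standard rate of related adverse events of grade 2 or higher is taken as 10%, and the rate to detect is 15%. The rule is stated in absolute counts: "We will consider an alarm when more than 21, 31, 41, and 51 patients show adverse events". On the error rates it says "Errors of both types are set at 5" per cent.

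Three parts of the SAP bear on whose events enter those counts:

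- **Timing.** SAP 7.1: "The interim analyses will occur after each consecutive group of another 102 evaluable patients has completed their treatments". SAP 10 agrees, and describes the total of 408 as the number left after drop-out.
- **Population.** SAP 7.2.3: "The safety population includes all patients who enter the study at study period T1". It continues: "Safety analysis will be done based on adverse event rates for the whole safety population regardless of their treatment assignments or actual treatments". SAP 5.4.1 expects about 500 consented patients. Those much improved after the run-in "will not be randomized and continue with long-term follow-up" (SAP 5.1).
- **Framing of the alarm.** SAP 10 introduces the alarm as concerning events related to the study treatment, and gives the expected stopping size under a 15% rate as "at 253 treated patients or less on average".

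The end of randomisation is also stated in two ways. SAP 5.5 stops at 408 randomised. SAP 6 continues until 102 per group have completed T1 to T4.

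Protocol 18.1.5 (safety monitoring paragraph) has a different rule: looks every 100 patients, with an alarm at more than 22, 32, 42 or 52.

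**The concern.** An absolute count has an error rate only for a known number of patients at risk. The SAP counts fit 102, 204, 306 and 408, but the looks are triggered by patients who finished treatment. Anyone who started and left has also been exposed, and a safety count would naturally include that person's events. The number at risk at a look then exceeds the number the count was built for. SAP 7.2.3 points to a larger group still.

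If the treatments run at the standard 10% rate, the DSMB could receive a suggestion to stop more often than the 5% it has been told. In the other direction, a board relying on a 5% chance of missing a 15% rate would be relying on a figure the counts do not deliver.

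The final look has a timing problem as well. If randomisation stops at 408 (SAP 5.5), any loss means 408 completers are never reached.

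**Working it through.** **Inputs from the documents.** Alarm if the cumulative number of patients exceeds 21/31/41/51; p0 = 0.10; p1 = 0.15; both errors 5% (SAP 10). Looks every 102 completers up to 408 (SAP 7.1, 10).

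**Assumed.** Loss of 5%, 10% or 15% among treated patients, because the plan gives no figure. Related-event rate q in never-randomised entrants, also not given.

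**Step 1: where the counts come from.** Fleming's upper limit at look g is n_g × p0 + 1.645 × √(N × p0 × (1 − p0)). With N = 408, √(408 × 0.09) = 6.06 and 1.645 × 6.06 = 9.97. The limits are 10.2 + 9.97 = 20.2, then 30.4, 40.6 and 50.8. Rounding up gives 21, 31, 41, 51, so the counts were built for 102/204/306/408.

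**Step 2: reproduce the stated 5%.** Exact recursion: carry the binomial distribution of the cumulative count forward, and at each look remove and add up the probability above the limit. At p = 0.10 and 102/204/306/408, the overall false-alarm rate is **4.98%**, of which 2.5% falls at the three interim looks. The stated 5% reproduces on the literal more-than reading. With Fleming acceptance bounds added it is 4.68%.

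**Step 3: slack.** 103 per look gives 5.7%, 104 gives 6.5%, 105 gives 7.4%. Smaller groups stay below 5% (100 per look: 3.7%).

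**Step 4: treated drop-outs counted at completer-timed looks.** The number treated at look g is 102g / (1 − loss). For example, 102/0.90 = 113.

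| Assumed loss | Treated at looks 1–3 | False alarm, interim looks | Overall, last look at 408 (SAP 5.5) | Overall, until 408 complete (SAP 6) |
|---|---|---|---|---|
| 0% | 102/204/306 | 2.5% | 4.98% | 4.98% |
| 5% | 107/215/322 | 5.0% | 6.4% | 9.8% (429) |
| 10% | 113/227/340 | 9.6% | 10.1% | 18.2% (453) |
| 15% | 120/240/360 | 17.4% | 17.5% | 31.2% (480) |

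Final sizes under SAP 6 are in brackets. Patients still in treatment at a look are not included.

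**Step 5: reachability of the fourth look.** With 408 randomised, completers number 408 × 0.95 = 388, 408 × 0.90 = 367 or 408 × 0.85 = 347. The trigger of 408 completers is not met.

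**Step 6: never-randomised entrants.** Take 500 − 408 = 92, or 23 per look, added to 102 treated at 10%. Overall false alarms are 5.0%, 5.8%, 6.8% or 9.1% for q = 0, 0.5%, 1% or 2%.

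**Step 7: type II error.** At p = 0.15 and 102/204/306/408 the rule alarms with probability 91.9%, so type II is 100 − 91.9 = **8.1%** (9.3% with acceptance bounds). Even a single look at 408 has no cut-off with both errors at 5%: more than 51 gives 4.2% and 8.7%; more than 50 gives 5.8% and 6.6%; more than 49 gives 7.8% and 4.9%.

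**Step 8: the protocol's rule.** More than 22/32/42/52 at 100/200/300/400 gives 2.6% false alarms and 86.1% detection.

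**The case against.** The best reply is that SAP 10 already implies its group. The alarm concerns events related to the study treatment, the expected sizes are in treated patients, and each look follows a recruitment group of 102. On that reading the group that triggers the look is the group counted, and 5% holds.

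Much of this stands. A reader might apply SAP 7.2.3 literally, count all 500 entrants at a common 10% rate, and infer a false-alarm rate of 42.5%. The documents do not support that. Never-randomised entrants receive none of the four treatments, so treatment-related events in them should be near zero, and at q = 0 the rate stays at 5.0%. SAP 10.1 does define relatedness more broadly (an event that "follows a reasonable temporal association with the study procedures"), so q need not be exactly zero, but the effect of a small q is modest.

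A reader might also take 31.2% as the risk of stopping the trial wrongly. It is not. The fourth look is the final analysis, when nothing remains to stop. The relevant figures are those for the interim looks, and at 5% loss these are still about 5%.

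The reply does not remove the point. Drop-outs are treated patients, so the treated-patients wording includes them while the completer trigger leaves them out. SAP 7.2.3 is an explicit rule that points away from the implied group. Protocol 22.2 keeps patients who stop an intervention in follow-up, but the looks are triggered by completed treatment, so such patients are still at risk without advancing the trigger.

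**Conclusion.** The concern holds in a limited form. The counts are correctly built for 102/204/306/408 patients; what is missing is a statement that these are the patients counted. Following the text as written can give interim false-alarm rates of about 5.0%, 9.6% or 17.4% against 2.5% by design. Those figures assume 5%, 10% or 15% loss, a uniform 10% rate, and treated drop-outs being counted. Never-randomised entrants add little, though SAP 7.2.3 should be reconciled with SAP 10.

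The type II statement is wrong whichever group is meant by the design sizes: about 8%, not 5%. It would be too generous to say that both stated error rates hold for one choice of group. Counting more patients lowers the type II error only by raising false alarms above 5%.

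Severity is minor to moderate. The alarm is advisory, the DSMB makes the recommendation, and over-counting errs towards safety.

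**What to change.** In SAP 10, with cross-references from 7.1 and 7.2.3:

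1. Define the alarm group as the first 102, 204, 306 and 408 patients who start a randomised treatment. Count every related event of grade 2 or higher in them from first treatment, whether or not they complete.
2. Take each look at the scheduled T4 date of the last patient in the group. The fourth look then takes place despite drop-out, under either randomisation stopping rule.
3. At each look, report events in all other entrants (never treated, or later starters) to the DSMB on a separate line.
4. Restate the type II error as about 8%.
5. Replace the counts and look sizes in Protocol 18.1.5 with those of the SAP.

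Rescaling the counts to T1 entrants (more than 25/37/50/62 at 125/250/375/500) is a weaker option. If never-randomised entrants have a 0–2% rate, detection of a 15% rate in treated patients falls to 44–54%.

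The cost is wording in two documents, with no new data or visits. The one real drawback is that related events in later starters enter the alarm count only at the next look, although the DSMB sees them on the separate line. The false-alarm rate returns to 4.98%; the type II error stays at about 8%.
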